The PI ([name]), assisted by the project manager, will be responsible for maintaining communication between the DSMB and the individual project staff. The DSMB will be responsible for monitoring the trial and making decisions about the termination of individual study arms or the study itself. The DSMB will review and approve the research protocol. They will also assess the progress of the trial, including the assessment of data quality, participant recruitment, accrual and retention, participant risk versus benefit, and study outcomes. Corresponding recommendations will be issued at all subsequent meetings. These recommendations will be based on the results and discussion of interim analyses, conducted at one-half, and three-fourths of the target same size. DSMB recommendations may be guided by statistical monitoring guidelines. The DSMB may recommend permanent suspension of enrollment, or temporary suspension pending protocol modification. Following each meeting, and the provision of recommendations and the response from the research team, the Principal Investigator and Project Manager will prepare progress reports to be submitted to the University of Pennsylvania Institutional Review Board and any other IRBs participating in the trial. Prior to submission to these IRBs, the progress reports will be approved by the DSMB chair.

c. Stopping Rules

The PI, in consultation with Co-Investigator and Faculty Statistician [name], has identified TWO trial stopping rules. The DSMB approved these stopping rules as grounds to terminate the trial:

- 1. Early evidence of undue inducement that distorts voluntary informed consent. To detect whether incentives represent undue inducement, the research team will test the statistical interaction between incentive size and risk perception on the outcome of enrollment in the parent RCT. A statistically significant interaction, in the direction that risk perception is less strongly associated with enrollment in higher-payment arms, would be grounds for terminating the trial or suspending a trial arm.

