- 2. Early evidence of unjust inducement by preferentially encouraging participation among participants with either (a) lower income, or (b) reduced financial well-being. Two interaction terms will be evaluated in separate models to avoid collinearity. Unjust inducement will be defined as a statistically significant interaction between (a) incentive size and annual household income, or (b) between incentive size and economic well-being, each on the outcome of trial enrollment. One or both of these interactions, if statistically significant in the direction that lower-income persons or persons with reduced economic well-being are more strongly motivated to participate by increasingly large payments, will be considered grounds for terminating the trial or suspending a trial arm.

During the trial we will conduct two interim tests of these interactions to evaluate evidence of undue or unjust inducement. In contrast to the final analyses, which will be structured as tests of non-inferiority, the interim analyses will be conducted as superiority tests of the interactions, such that rejection of the null hypothesis indicates evidence of the presence of an interaction between incentive size and one of our three primary covariates. The interim tests will be conducted after 50% and 75% of the data have accrued within both BASC and MOVE IT and use 1-sided significance levels of 0.0055, and 0.0219. The DSMB is empowered to stop the trial early if the lower confidence bound exceeds 2.0, thus protecting against undue or unjust inducement.

The DSMB may also wish to consider increased rates of therapeutic misconception as grounds for early termination of the trial. The research team will compare responses to the trial's measure of the construct of therapeutic misconception across the three trial arms. While no pre-specified statistical monitoring guidelines are proposed for this measure, DSMB members may consult with [name], with whom the therapeutic misconception tool for the trial has been developed, for guidance on interpretation of the data provided in the open statistical report.

d. Adverse Events

As this is a minimal risk study, we do not anticipate adverse events; however, we will report all adverse events to the Data and Safety Monitoring Board.

e. Clinicaltrials.gov

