	secondary	risk score distributions. We found that in the Ambulation trial the
	analysis of the	risk score mostly (>85%) clumped on 0, and in the smoking trial the
	risk score and	score is extremely right skewed. To better handle this sparsity of
	incentives where	data we planned a secondary analysis in which we treat the risk
	risk score is	scores as binary and compare the inferences.
	treated as a	
	binary variable (0	
	and >0).	

VI. Final Statiscal Analysis Plan

1. Background and rationale

This study is designed to provide the first-ever real-world tests of a broad range of intended and unintended consequences of financial incentives for research participation. It will do so through the conduct of two separate, but similarly designed, embedded randomized trials within actual parent clinical trials. It is our hope the findings from this study will inform research regulations and guide the use of incentives in future RCTs so as to expedite medical innovation and improve health

2. Objectives and hypotheses

The aims of this study are to (1) determine if the ethical concerns with incentives for research participation actually manifest; and (2) assess the possible scientific and ethical benefits of financial incentives for RCT participation.

We hypothesize that research incentives will:

- Augment participants' perceptions of risk without disproportionately encouraging economically disadvantaged participants to enroll
- Demonstrate an increased enrollment fraction in the parent trials, thereby enhancing the scientific value and validity of the research by augmenting the precision of the studies

3. Design and randomization

RETAIN comprises two prospective randomized controlled trials, embedded within two parent trials conducted in parallel, each comparing three intervention arms. Arms vary by the amount of the financial incentives that are offered to potential participants. Amounts offered differ on a per trial basis determined by the relative time and effort being asked of the participant for each parent trial. Assignment to arms is determined by computerized random-number generation with block randomization using variable block sizes of 3 and 6. Participants in both embedded trials have a 33.3% probability of being assigned to each RETAIN arm.

a. BASC Trial

• The Behavioral Activation and Varenicline for Smoking Cessation in Depressed Smokers Study (BASC) (NCT 02378714)

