the outcome of enrollment in the parent trials. We will test two interactions, each in a separate model to avoid collinearity, to determine if incentives represent unjust inducements: that between incentive size and the primary covariate of annual household income, and that between incentive size and the primary covariate of economic well-being. All analyses will be stratified by parent study.

Analyses of interaction terms will be structured as tests of non-inferiority. The null hypothesis, for both trials, will be that the use of incentives meets criteria for undue or unjust inducement. We can reject the null, and conclude the absence of undue or unjust inducement, if the interaction terms are "small" according to pre-specified criteria (in technical terms, the inferiority margin). Said a different way, our analyses are designed to determine if we can exclude the possibility that incentives represent undue or unjust inducements if the resulting interaction terms are sufficiently small. Specifically, we will use one-sided alpha levels of 0.05 to exclude, with 95% confidence, the possibility that any of these interaction odds ratios are >2.0.

We will explore temporal trends in incentives' effects over the study period using stratified analyses. If temporal trends are noted, as may occur if prospective patients learn of the incentives used in these studies, we will adjust for their influence by entering time as a covariate, modeled as a spline. We will evaluate potential effect modifiers (variables in Table 1) using stratified analyses. If differences among strata appear, we will formally test their corresponding interactions with the incentive amount.

TABLE 1 FACTORS FOR ADJUSTMENT AND EXPLORATION OF EFFECT MODIFICATION

Potential factors for adjustment			
Patient level covariates	Variable coding or definition		
• Age	Continuous		
• Gender	Binary		
• Race	Categorical		
Marital status	Categorical		
Education	Categorical		
Income	Categorical		
Economic well-being	Categorical		
Prior research participation	Categorical		
Attitudes towards research:	Continuous, measured using the Research Attitudes Questionnaire-7 (RAQ- 7).		

6. Secondary analysis

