The target enrollment of 576 patients in each RETAIN sub-trial was determined based on the primary goal of ruling out the possibility that incentives represent an undue inducement. Statistically, the presence of an undue inducement is represented by the interaction term between incentive amount and risk on the outcome of enrollment in the parent trial. Thus, we seek to rule out the possibility that the odds ratio associated with this interaction term is appreciably greater than a null value. To facilitate such a power estimation, we considered groups of participants with greater or less than the median level of risk perception who will be randomized to the highest incentive versus the lowest incentive. With an overall sample size of 576 participants in each parent study involved in the RETAIN trial, we assumed that 192 participants would be randomized to each of the 3 incentive arms. Assuming that randomization balances the incentives distribution within each risk-perception group, 96 participants will be assigned to each of the 3 incentives within both the high and low risk-perception groups. Among patients assigned to receive \$0, we set the OR contrasting the odds of enrollment between riskperception groups to 1, such that the OR for those assigned to receive the highest incentive (\$300 or \$500, in MOVE IT and BASC, respectively) represents the interaction odds ratio. We assume a true interaction OR of 1, and use a one-sided significance level of 0.0427 such that the upper 95.73% confidence limit on the observed OR falls entirely below the non-inferiority threshold. If the enrollment rate in the parent trials is 50%, we will have at least 80% power to rule out undue inducement, as represented by an interaction odds ratios of 2.0 or greater. However, because we will actually analyze risk as a continuous variable and incentive size as a 3-level variable, our true power will be greater than the estimates reported here. Similar analyses suggest similar levels of power to rule out the unjust inducement interaction terms.

8. Data Safety & Monitoring Board (DSMB)

We have chartered a DSMB to monitor RETAIN, with purview over both embedded trials, for the expressed purpose of evaluating evidence of undue or unjust inducement. Any serious adverse events, protocol deviations/violations, and unanticipated events will be reported to the IRBs with oversight of recruiting sites, the DSMB, and The National Cancer Institute.

9. Stopping Rules

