Trial stopping rules were approved by the Data Safety and Monitoring Board for the following events:

a. Undue inducement

To detect if incentives represent undue inducement that could distort voluntary informed consent, the research team will test the statistical interaction between incentive size and risk perception on the outcome of enrollment in the parent RCT.

b. Unjust inducement

To assess the presence of unjust inducement, or preferential participation among participants with either (a) lower income, or (b) reduced financial well-being, two interaction terms will be evaluated in separate models to avoid collinearity. Unjust inducement will be defined as a statistically significant interaction between (a) incentive size and annual household income, or (b) between incentive size and economic well-being, each on the outcome of trial enrollment. One or both of these interactions, if statistically significant in the direction that lower-income persons or persons with reduced economic well-being are more strongly motivated to participate by increasingly large payments, will be considered grounds for terminating the trial or suspending a trial arm.

10. Timing of analysis and adjustment of significance level

Interim analyses will be conducted after 50% and 75% of the data have accrued within each the BASC and MOVE IT trials. In contrast to the final analyses, which will be structured as tests of non-inferiority, the interim analyses will be conducted as superiority tests of the interactions, such that rejection of the null hypothesis indicates evidence of the presence of an interaction between incentive size and one of our three primary covariates. We will use 1-sided significance levels of 0.0055, and 0.0219.

11. Personnel

Interim analyses will be performed by the trial's primary statistician who will conduct all analyses blinded to trial arm. Investigators, the project manager, and the DSMB will remain blinded to treatment arm through completion of analyses. The data manager and faculty statistician have been unblinded as was necessary to perform essential functions of their roles.

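### Final Protocol 11.c gives two different interim stopping thresholds for the same interaction tests, one with a null odds ratio of 1 and one of 2.0, and the SAP carries only the first

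*Combined protocol and SAP*

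**What the plan says.** Final Protocol 11.c lists two stopping rules that the DSMB approved. Rule 1, on undue inducement, can end the study or pause one of its arms: "A statistically significant interaction, in the direction that risk perception is less strongly associated with enrollment in higher-payment arms, would be grounds for terminating". Rule 2, on unjust inducement, uses statistical significance in the same way for the interactions of incentive size with income and with economic well-being.

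The section then contrasts the interim looks with the final non-inferiority analysis. The looks, at 50% and 75% of the data, are superiority tests in which "rejection of the null hypothesis indicates evidence of the presence of an interaction between incentive size and one of our three primary covariates". The one-sided levels are 0.0055 and 0.0219. The sentence that follows those levels is: "The DSMB is empowered to stop the trial early if the lower confidence bound exceeds 2.0, thus protecting against undue or unjust inducement". It gives no confidence level for the bound.

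Final SAP section 9 says that the undue-inducement interaction will be tested and defines unjust inducement by statistical significance. Section 10 repeats the superiority framing and the levels: "We will use 1-sided significance levels of 0.0055, and 0.0219". Neither mentions 2.0. In the SAP that value belongs to the final analysis, where section 5.c uses a one-sided test "to exclude, with 95% confidence, the possibility that any of these interaction odds ratios are >2.0", and to the power calculation in section 7.b, where undue inducement is "represented by an interaction odds ratios of 2.0 or greater".

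Final Protocol 11.b adds: "DSMB recommendations may be guided by statistical monitoring guidelines".

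**The concern.** A test for the presence of an interaction has a null OR of 1. Rejecting it at a given one-sided level is the same as finding the matching lower confidence bound above 1. A lower bound above 2.0 rejects a different null, OR of 2.0 or less. The rules are nested, since any result that meets the 2.0 rule also meets the significance rule at the same level. They disagree whenever the lower bound falls between 1 and 2. In that range one sentence of 11.c finds a reason to stop, while the sentence that empowers the DSMB to stop is not met.

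This matters because the procedures for monitoring and stopping are one of the five reasons that Final Protocol 8.g gives for calling the study minimal risk. The study also withholds the incentive randomization from participants and runs under a waiver of consent. A reader should be able to tell which threshold was approved and which was applied.

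**Working it through.** **The plan's own levels.** The interim levels 0.0055 and 0.0219 (Final Protocol 11.c, SAP 10) and the final level 0.0427 (SAP 7.b) correspond to z = 2.543, 2.016 and 1.720. With information fractions 0.5, 0.75 and 1 and correlations sqrt(t_i/t_j), the chance of crossing any of them under the null is 0.04997, or 0.0500. An O'Brien-Fleming-type spending function at one-sided 0.05 gives 0.00557, 0.0219 and 0.0427. So the levels reproduce as one sequence, but they do not say which null value applies at the looks.

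**Assumptions for the illustration.** From SAP 7.b: 192 per arm, a median split of risk perception, 96 per cell, 50% enrollment. Added here: the 2.0 bound uses the stated interim levels, that is, one-sided bounds of 1 − 0.0055 = 99.45% and 1 − 0.0219 = 97.81%.

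**Standard error of the log interaction OR** (highest against lowest incentive, high against low risk, four cells): SE = sqrt(4/(n × 0.25)).
- Full sample, n = 96: sqrt(4/24) = 0.408
- 50% look, n = 48: sqrt(4/12) = 0.577
- 75% look, n = 72: sqrt(4/18) = 0.471

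**Observed OR needed.** Significance rule: exp(z × SE). 2.0 rule: 2 × exp(z × SE).

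| Look | Significance rule | 2.0 rule |
|---|---|---|
| 50% | exp(2.543 × 0.577) = 4.34 | 8.68 |
| 75% | exp(2.016 × 0.471) = 2.59 | 5.17 |

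At a common level the ratio is exactly 2, whatever the SE. For example, an observed OR of 3.5 at the 75% look has a lower bound of 3.5/2.59 = 1.35, which meets one rule and misses the other.

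**Chance of crossing by the 75% look.** The normal-theory figures use a bivariate normal with correlation sqrt(0.5/0.75) = 0.816. The binomial simulation adds 0.5 per cell, applies the OR to the high-risk, high-incentive cell and keeps 50% enrollment in the other three.

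| True OR | Normal theory, significance vs 2.0 rule | Binomial, significance vs 2.0 rule | Binomial gap (points) |
|---|---|---|---|
| 2 | 30% vs 2.4% | about 28% vs 2% | 28 − 2 = 26 |
| 3 | 63% vs 13% | about 60% vs 11% | 60 − 11 = 49 |
| 4 | 83% vs 30% | about 78% vs 25% | 78 − 25 = 53 |

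Because the rules are nested, the gap is the chance that the significance rule is met and the 2.0 rule is not. With no interaction, normal theory gives 2.36% against 0.03%. The 2.4% at a true OR of 2 is simply the alpha spent over the two looks.

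**Limits.** The planned model uses continuous risk and ordered incentive, and the unit of the OR is not given. The four-cell SE does not reproduce the stated power of at least 80%: log 2/0.408 − 1.720 = −0.02, which is about 49%. The 2/17/2020 entry in Changes to Statistical Analysis Plan also reports, for the Ambulation trial (MOVE IT by context), a "risk score mostly (>85%) clumped on 0, and in the smoking trial the" score extremely right-skewed, so no median split exists there. With an 85/15 split of zero against above zero (SE 0.572 at full sample), the required ORs are 7.8 and 3.8 against 15.6 and 7.6. At a true OR of 4 the binomial crossing chances are about 43% against 10%. That coding is a later secondary analysis, not the planned interim test.

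**The case against.** The strongest defense is that the wording is permissive. A significant interaction is only a ground for stopping, the DSMB is empowered rather than obliged to stop, and 8.g lets it weigh a range of outcome data. On that view the 2.0 sentence could be an added power. The discretion is real, but it does not turn a null of 1 and a null of 2.0 into one threshold. The added power would also be empty if significance already suffices, and no passage states that reading.

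It can also be said that the confidence level is not really missing, because the one-sided levels stand in the sentence just before the bound. That is fair. Bounds of 99.45% and 97.81% are the natural reading and are used above, but they leave the two null values different.

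A reader might infer three stronger things that the documents do not support.
- That a decision to continue certified either no significant interaction or a lower bound not above 2.0. It certified neither, because both rules leave the decision to the DSMB. No passage shows a result between the two thresholds.
- That 2.0 is certainly leftover text. The superseded Original Protocol framed the interim tests as non-inferiority tests against 2.0, while the Original SAP already had superiority tests without it. The current sentence was edited to say lower bound, so carry-over and deliberate choice are both possible.
- That the final inference is compromised. The primary outcome and the final non-inferiority criterion do not depend on this sentence.

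**Conclusion.** Wrong as written: an internal inconsistency in a decision threshold, within the current Final Protocol 11.c and between it and SAP sections 9 and 10. The contradiction rests on the text alone and needs no calculation.

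The factor of two in the observed OR depends only on using the same confidence level for both rules. The crossing chances also rest on the median split, four-cell SE and 50% enrollment, so they show scale and are not operating characteristics of the planned model. The point should be fixed because it concerns a safeguard that the protocol relies on. This review does not say which threshold should govern.

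**What to change.** Reconcile Final Protocol 11.c with SAP sections 9 and 10 to the single interim threshold that the DSMB actually approved. State its null value, direction and confidence level identically in both documents, for example: *the threshold is met when the one-sided lower confidence bound, at [level for each look], for the interaction odds ratio, coded so that values above 1 are the harmful direction, exceeds [approved null value]*. Remove whichever wording does not match, and add a change-log entry.

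Interim analyses had already been held by the 2/17/2020 change-log entry, so new wording cannot alter those looks and should record the approved rule rather than create one. For each look in BASC and MOVE IT, report which threshold and confidence level were applied, with the interim interaction estimates and bounds.

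The cost is a few sentences in each document, one log entry and DSMB confirmation of the wording. No new data are needed.

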The RETAIN study involves no more than minimal risk to participants for 5 reasons: (1) incentives in the amounts we are proposing are given to patient subjects as part of many ongoing or completed trials;³⁵ (2) the evidence available to date suggests that the ethical concerns identified with incentives may not arise, (3) we have established robust procedures for monitoring whether those ethical concerns do in fact arise and for stopping the incentives study if so, (4) the patients would be approached to participate in the parent RCTs without the incentive study, and (5) their participation in the RETAIN study will not affect which treatment they receive in the parent RCTs.

To the extent that it is avoidable, the use of deception will have no adverse effects on welfare, and all adverse effects will be minimized.

Adverse events from the incomplete disclosure of the randomization of participants to different levels of incentives will be minimized through the debriefing process. Patients will be debriefed following their decision to enroll in the parent trial immediately before their first treatment visit (BASC) and within the same session as the initial approach (MOVE IT). This debriefing will therefore happen within a few days (at maximum) of the deception, and will provide participants with full disclosure of the research and with an opportunity to withdraw their participation or their data. Patients who decline to participate in the parent trials will not be debriefed. The Principal Investigator will be directly responsible for identifying and reporting adverse events to the IRB of record and respective IRBs at the four sites and the DSMB.

Additional oversight will be provided by the following: (1) a DSMB that will have the flexibility to adjudicate trial continuation or cessation based on a compendium of outcomes data; (2) two advisory boards comprised of experts in relevant disciplines including research ethics and regulations that will assist the investigators in addressing any unforeseen ethical and scientific issues during the trial's conduct.

The value of the study is sufficient to warrant waiving some aspects of the requirement for full disclosure in the informed consent process.

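### Final Protocol 11.c states two incompatible interim stopping criteria and credits protection to the lower-bound rule, which is crossed in only 2.4% of trials when the interaction odds ratio is 2.0

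*Combined protocol and SAP*

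**What the plan says.** Final Protocol 11.c makes a statistically significant interaction, in the harmful direction, grounds for terminating the trial or suspending an arm. The interactions are incentive size with risk perception (undue inducement), and with household income or economic well-being (unjust inducement). On timing: "The interim tests will be conducted after 50% and 75% of the data have accrued". The interim tests "use 1-sided significance levels of 0.0055, and 0.0219", and they are superiority tests, so that "rejection of the null hypothesis indicates evidence of the presence of an interaction". The same paragraph ends with another threshold: "The DSMB is empowered to stop the trial early if the lower confidence bound exceeds 2.0, thus protecting against undue or unjust inducement".

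Final SAP 9 and 10 repeat the significance criterion and the same two levels. They do not mention a lower bound of 2.0. That value is the margin of the final non-inferiority test, which aims to exclude "the possibility that any of these interaction odds ratios are >2.0" (Final SAP 5.c).

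Final Protocol 8.g gives five reasons why the undisclosed randomisation is minimal risk. The third is that "we have established robust procedures for monitoring whether those ethical concerns do in fact arise and for stopping the incentives study if so". Neither document states the probability that an interim rule would be crossed. The only power figure, at least 80% in Final SAP 7.b, is for the final test.

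**The concern.** A lower bound above 1 and a lower bound above 2.0 are different hypotheses. A result can satisfy the first and fall far short of the second, and the text does not say which one governs. The claim of protection is attached to the stricter rule. That rule asks for confident evidence that the interaction already exceeds the level the plan regards as unacceptable, so it is poorly placed to act when the interaction sits at that level.

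Two things are at stake. A DSMB holding an interim result between the two thresholds would have no settled rule. And the IRB and DSMB are offered the monitoring as a reason for accepting incomplete disclosure without being told how often it would act.

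**Working it through.** **Inputs.** Looks at 50% and 75% of the data; one-sided levels 0.0055 (z = 2.543) and 0.0219 (z = 2.016) (Final Protocol 11.c, Final SAP 10). From Final SAP 7.b: "192 participants would be randomized to each of the 3 incentive arms", a median split on risk perception giving 96 per cell, highest incentive versus $0, 50% enrolment, and a final one-sided level of 0.0427 (z = 1.720).

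**Assumptions of this check.** The lower bound uses the same level as its look, since 11.c gives no separate confidence level. OR 2.0 compares highest with lowest incentive, as 7.b implies. Figures are for one interaction in one parent trial.

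**The plan's own power figure.** Power = Φ(ln 2/SE − 1.720). With both arms' odds ratios estimated (four cells), SE = √(4/(96 × 0.25)) = 0.408 and power is 49%. With the $0-arm OR treated as known (two cells), SE = √(2/(96 × 0.25)) = 0.289 and power is 75%. Neither reproduces at least 80%. That is a separate matter, but it shows that 7.b can be read with either SE, so both are carried below.

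**Origin of the levels.** Under no interaction, cumulative crossing at 0.0055, 0.0219 and 0.0427 is 0.0055, 0.0236 and 0.0500. This matches O'Brien-Fleming-type spending of one-sided 0.05.

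**Interim SE, four cells.**
- Look 1: 48 per cell, √(4/(48 × 0.25)) = 0.577.
- Look 2: 72 per cell, √(4/(72 × 0.25)) = 0.471.

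**Observed OR needed.**
- Superiority: exp(2.543 × 0.577) = 4.3, then exp(2.016 × 0.471) = 2.6.
- Lower bound above 2.0: twice these, 8.7 and then 5.2.

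**Crossing probability.** At look k it is Φ(ln(OR/θ)/SE − z), with θ = 1 for superiority and θ = 2 for the lower bound. For superiority at OR 2:
- Look 1: Φ(0.693/0.577 − 2.543) = Φ(−1.34) = 9.0%.
- Look 2: Φ(0.693/0.471 − 2.016) = Φ(−0.55) = 29.3%.
- Either look, bivariate normal with correlation √(0.50/0.75) = 0.816: 30.0%.

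For the lower bound at OR 2, ln(OR/θ) = 0, so the result is the cumulative alpha of the two looks, 2.4%, whatever the SE.

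Cumulative crossing by look 2:

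| True OR | Superiority, four-cell | Superiority, two-cell | Lower bound > 2.0, four-cell | Lower bound > 2.0, two-cell |
|---|---|---|---|---|
| 2 | 30% | 53% | 2.4% | 2.4% |
| 3 | 63% | 90% | 13% | 22% |
| 4 | 83% | 98% | 30% | 53% |

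Binomial simulation (200,000 trials, four cells, OR 2) gives 28.7% for superiority and 2.2% for the lower bound.

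**Sensitivity of the superiority figure at OR 2.**
- Risk perception in MOVE IT: the SAP change log reports more than 85% of scores at 0. With an assumed 85/15 split the SEs are 0.808 and 0.660, and crossing is 17% (37% at OR 3).
- Enrolment of 20% instead of 50%: 21%.
- OR 2.0 read as per incentive step: 83%.
- All three interactions truly at 2.0 and independent: 1 − (1 − 0.300)³ = 66% cross on at least one. The lower-bound rule gives 1 − (1 − 0.0236)³ = 7%.

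**The case against.** The strongest reply is that the boundary is not the whole safeguard. Final Protocol 11.b says DSMB recommendations may be guided by statistical guidelines, lets the board review risk against benefit and study outcomes, and allows temporary suspension. Section 8.g gives it latitude to weigh a body of outcome data, and consenting participants are debriefed and may withdraw. This stands. The figures above are probabilities of crossing a boundary, not of the board failing to act. A reader might infer that inducement at OR 2 would usually run undetected to full enrolment; the documents do not support that.

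A reader might also take the 2.4% as proof that the interim samples are too small. It is not: it equals the cumulative alpha at any sample size when the truth sits on the threshold. What it shows is that a bound placed at the limit cannot guard that limit.

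The 30% is conditional too. The four-cell SE is this check's choice. It suits an interaction in which both odds ratios are estimated, but 7.b can be read as the two-cell case. The 17% applies only to risk perception in MOVE IT, and the zero/non-zero split is a secondary analysis.

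Finally, one might conclude that the strict levels are wrong and should be loosened. Stopping because an interaction seems present cannot create a false claim that it is absent, so the final test does not need them. But a false stop would end a trial meant to settle this very question. A one-sided 0.05 trigger at each look raises detection at OR 2 to 48%, while false alarms rise from 2.4% to 7.4% per interaction, and from about 7% to about 21% over three independent interactions. That is a trade-off on which statisticians may differ, and no requirement in the documents is breached by the present levels.

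**Conclusion.** The point holds as a contradiction and an unsupported claim of protection. Section 11.c carries two interim criteria that cannot both govern, and its protective wording is attached to the one crossed in 2.4% of trials at OR 2.0 and in about 13% at OR 3 (22% with the two-cell SE). The superiority rule, which the SAP also uses, is crossed in about 30% at OR 2 and 63% at OR 3. Those figures assume one interaction in one parent trial, a median split, highest incentive versus $0, 50% enrolment and the four-cell SE. The OR 2 range is about 17% to 53%, and higher if several interactions are present or OR 2.0 is meant per step. The 2.4% needs no variance assumption, only that the bound uses the look's own level. If a one-sided 95% bound were used at both looks, the same reasoning gives 7.4%.

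The superiority rule is therefore a moderate safeguard at the limit and a better one beyond it. The plan should say so in figures.

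**What to change.** 1. In Final Protocol 11.c, delete the condition that the lower bound exceed 2.0. Keep the superiority test against OR 1 at 0.0055 and 0.0219, so that 11.c agrees with Final SAP 9 and 10. Show the DSMB the estimate and confidence interval at each look.
2. State that rule's crossing probabilities at OR 2 and OR 3, with their assumptions, and say whether OR 2.0 is per step or highest versus lowest incentive.
3. Reword the closing claim of 11.c and the third reason in 8.g to match those figures, and note the DSMB's wider discretion.
4. Optional: put the one-sided 0.05 review trigger to the DSMB with its false-alarm rates.

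The cost is protocol and SAP wording, a note to the DSMB, and a less favourable stated figure. The final test is unchanged. The change log entry of 2/17/2020 shows that interim analysis had already taken place, though not whether both looks were complete. The correction therefore applies to any remaining look and to how the protection is described.
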